Diabetic foot ulceration (DFU) is a common and largely preventable complication. [1] While most of these ulcers can be treated successfully, some will persist and become infected. Ultimately, nearly one fifth of patients with infected lower-extremity diabetic ulcers will require amputation of the affected limb, resulting in staggering costs for both the patient and the healthcare system. Prevention by identifying people at higher risk is the key for better clinical management of such patients. It is not uncommon for patients suffering from diabetes to have concomitant lower extremity edema or even venous insufficiency[2-4] and they subsequently may benefit from graduated compression[5-7]. However, because of the common association of peripheral arterial disease (PAD) in patients with diabetes[8-10], most clinicians are reluctant to apply compressive dressings in fear of exacerbating the symptoms of PAD and the possible resulting gangrene[11].

Unfortunately, this area has received comparatively little attention from industry, academia, or insurance providers. A novel micro-mobile intermittent pneumatic foot compression device (AVEX Footbeat, Inc.) offers alternative means providing lower extremity compression. This device is portable and can be used in ambulatory settings providing increased venous blood and relief from concomitant lower extremity edema.

Section D: Purpose and Objectives

The purpose of this study is to conduct an observational study with N=30 patients to assess whether this micro-mobile foot compression device can help reduce lower extremity in patients with both diabetes and lower extremity edema without compromising the vascular supply.

The main purpose of this study is to determine if the device lessens edema. This study will also evaluate a new research device to see if it may help prevent diabetic foot ulcers. Additionally, it may potentially help delay progression of foot disease and produce a better quality of life by providing a better blood flow to foot and ankle.

Primary Endpoints: Reduction in lower extremity edema at 4 weeks of continuous device usage. Peripheral edema will be measured at baseline, 48 hours, 1 week and 4 weeks. Peripheral edema will be directly measured by traditional volume change assessment and indirectly by skin perfusion pressure assessment.

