Secondary Endpoints: 1) Improvement in balance and fall risk as measured at baseline and 4 weeks. 2) 48 Hours of continuous daily physical activity using a validated body worn sensor as measured at baseline and 4 weeks. 3) Gait assessment at baseline and 4 weeks.

Specific Aim and Hypothesis

Aim 1. To assess the effectiveness of a micro-mobile foot compression device that provides mild compression to help reduce peripheral edema as compared to baseline in patients with both diabetes and lower extremity edema in a four-week observational clinical trial of 30 patients.

Hypothesis 1: The micro-mobile foot compression device will result in edema reduction when compared to baseline peripheral edema for the study population.

Aim 2. To assess the effect of micro-mobile foot compression device on the macro and micro lower extremity circulation as measured by Ankle Brachial Index (ABI) and Skin Perfusion Pressure (SPP) Measurements.

Hypothesis 2: The micro-mobile foot compression device will help improve macro and micro- circulation in the lower extremity of patients with diabetes and lower extremity edema as compared to baseline. We expect to see positive changes in ABI and SPP measurements.

Aim 3. To assess the effect micro-mobile foot compression device on the quality of life quantified using the validated, international quality of life assessment survey SF12, fear of falling quantified by FES-I, and risk of falling assessment quantified by gait, balance and spontaneous daily physical activity of patients with diabetes and lower extremity edema.

Hypothesis 3. The micro-mobile foot compression device will improve the quality of life, lower the risk of falling, lower fear of falling, and improve activity level of patients as compared to baseline assessments.

Section E: Protocol Risks/Subjects

E1. Risk Category

Category 2: Research involving greater than minimal risk, but presenting the prospect of direct benefit to the individual subjects.

E2. Subjects

Gender:

Both

Age:

Adult (18-64 yrs), Geriatric (65+ yrs)

Ethnicity:

All Ethnicities

Primary Language:

English, Spanish

Groups to be recruited will include:

Patients

Which if any of the following vulnerable populations will be recruited as subjects?

Vulnerable populations require special protections. How will you obtain informed consent, protect subject confidentiality, and prevent undue coercion?

E3. Pregnant woman/fetus

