Will pregnant women and/or fetuses (as described in 45 CFR 46 Subpart B) be enrolled in the research?

No

E4. Neonates

Will neonates of uncertain viability or nonviable neonates (as described in 45 CFR 46 Subpart B) be enrolled in the research?

No

E5. Children

Will children be enrolled in the research?

No

Section F: Design/Procedure

F1. Design

Select one category that most adequately describes your research:

c) Pilot

Discuss the research design including but not limited to such issues as: probability of group assignment, potential for subject to be randomized to placebo group, use of control subjects, etc.

In this proof of concept, intent to treat trial, 30 consecutive patients with diabetes and lower extremity edema will be recruited from the outpatient clinic at Baylor College of Medicine. Patients will be consented per the local Institutional Review Board's guidelines and approval for this study.

Inclusion Criteria:

a) Males or females age 18-90 years old with history of type 1 or 2 diabetes and the ability and willingness to provide Informed consent b) Patients at risk of developing diabetic foot ulcers c) Patient is willing to participate in all procedures and follow up evaluations necessary to complete the study. d) Patients who have undergone lower extremity surgery / amputation may be enrolled into the study at the clinical judgment of the Investigator

Exclusion Criteria:

a) Patients with severe peripheral vascular disease (ABI or ankle brachial systolic pressure index <0.5) b) Patients with diabetic foot ulcers in the plantar foot region c) Patients with active wound infection, or untreated osteomyelitis d) Patients currently on immunosuppressive drugs. e) Pregnant or breastfeeding females. (standard urine pregnancy done on women during physical exam procedures) f) Acute fractures of the foot g) Acute heart failure h) Participation in an interventional Study within the last 30 days i) Non-ambulatory or unable to stand without help or walk a distance of at least 6 feet without assistance. k) Patients with major foot amputation. j) Patients who are unable or unwilling to participate in all procedures and follow up evaluations h) Patients with major foot deformities which won't fit in the diabetic shoes

F2. Procedure

Following is a summary of study procedures:

Study Day 0 (initiation), Visit 1 The following baseline values will be assessed and documented.

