The researchers will take digital photographs of you and videotape you and your feet during the study to monitor progress or deterioration (worsening) due to intervention. This is done using a normal digital camera for visual images and a thermal (heat sensitive) camera for thermal images. Both these methods are non-invasive. **We will NOT blur your face out in the photographs/videos. While we do all our efforts to mask your face in some cases (for example, journal policy) this may not be practical. We will only use videos and photos of you for scientific presentations or scientific publications. Initial your decision below.

I agree to have my photographs/videotape presented in scientific presentation or scientific publication

I do NOT agree to have my photographs/videotape presented in scientific presentation or scientific publication

Please provide below your Emergency contact information:

Contact name: _____

Relationship: _____

Phone number: _____

Section G: Sample Size/Data Analysis

G1. Sample Size

How many subjects (or specimens, or charts) will be used in this study?

Local: 50 Worldwide: 50

Please indicate why you chose the sample size proposed:

This is an initial proof of concept pilot study. The results of this study will allow for the calculation of an appropriate sample size for a larger proof of superiority (over current standard of care) trial.

G2. Data Analysis

Provide a description of your plan for data analysis. State the types of comparisons you plan (e.g. comparison of means, comparison of proportions, regressions, analysis of variance). Which is the PRIMARY comparison/analysis? How will the analyses proposed relate to the primary purposes of your study?

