Statistical Analysis - This study includes three hypotheses. To examine whether the proposed micro-mobile foot compression device will result in a edema reduction compared to the baseline (H1), we will use ANOVA and Fisher's exact tests for intra-subject rate of edema reduction using the outcome explained before. Multivariate and multiple linear regression test will be used for testing the effects of confounding factors including age, gender, BMI, foot insensitivity, etc. Additional, paired t-test will be used to examine whether amount of edema reduction at the end of study is significant compared to baseline. We will use Pearson correlation of coefficient and Fisher's exact tests to examine whether severity of neuropathy has any significant association with the rate of edema reduction. Finally, we will use multiple linear regression model to examine whether subject's level of activity, BMI, ABI, Skin perfusion pressure, and micro-mobile foot compression device are independent predictors for the rate of edema reduction.

To examine whether the proposed sock will help improve macro and micro-circulation in the lower extremity of patients (H2), we will use the similar analytical plan explained above by considering change in Skin perfusion pressure and ABI as dependent variables. For identifying the predictors, we will use multiple linear regression model and Anova (n-way). The independent variables will be severity of neuropathy quantified using Semmes Weinstein Monofilament, the level of activity, BMI, and age.

To examine whether the proposed socks will improve the activity level and quality of life (H3), we will use ANOVA multivariate test. The dependent variables will be number of total steps per day, duration of walking and standing, duration of longest episode of walking (i.e. continuous walking without stop), number of walking episode, duration of sit-to-stand and stand-to-sit postural transition, and SF12. We will use multiple linear regression model and multi-variant test to examine the effect of confounding parameters such as weather condition, BMI, age, etc.

Section H: Potential Risks/Discomforts

H1. Potential Risks/Discomforts

Describe and assess any potential risks/discomforts; (physical, psychological, social, legal, or other) and assess the likelihood and seriousness of such risks:

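### The H1 regression lists the device as a predictor although every patient receives it, and Fisher's exact test is named for a within-patient comparison

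*Combined protocol and SAP*

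**What the plan says.** The primary endpoint in Section D is "Reduction in lower extremity edema at 4 weeks of continuous device usage". Specific Aim 1 assesses the device "as compared to baseline in patients with both diabetes and lower extremity edema in a four-week observational clinical trial of 30 patients", and F1 (Design) states that "30 consecutive patients with diabetes and lower extremity edema will be recruited from the outpatient clinic". No control, sham or untreated group is described. F2 (Procedure) has the insole handed to the subject at Visit 1 and describes no subset that goes without it. G1 gives the sample size as 50, whereas the aims and F1 give 30.

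For H1, G2 (Data Analysis) names several analyses. Three matter here:

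- ANOVA and Fisher's "exact tests for intra-subject rate of edema reduction using the outcome explained before".
- A paired comparison: "Additional, paired t-test will be used to examine whether amount of edema reduction at the end of study is significant compared to baseline".
- A multiple linear regression to examine whether "level of activity, BMI, ABI, Skin perfusion pressure, and micro-mobile foot compression device are independent predictors for the rate of edema reduction".

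G2 uses Fisher's test a second time, together with a Pearson correlation, for the association between neuropathy severity and edema reduction across patients.

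**The concern.** Two of the analyses named for H1 do not fit a single-arm before-after design.

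First, a regression can assess a predictor only if it varies between patients. Receipt of the device does not vary. The plan nevertheless promises to say whether the device independently predicts edema reduction. A reader of the results could take a printed coefficient, or its absence, as evidence about the device when it is neither.

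Second, Fisher's exact test compares proportions in independent groups. Here the two sets of observations come from the same patients, so the test ignores the pairing. G2 also defines no yes/no edema outcome to which an exact test could apply. The edema assessment in F2 lists uncategorised clinical signs with circumferences, or water displacement.

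At stake are a claim that the design cannot deliver and, if edema is dichotomised, a probable loss of power in one of the H1 tests.

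**Working it through.** The plan gives no alpha, power, effect size or SD, so it has no figure of its own to reproduce. Both checks use n=30 (aims, F1) and n=50 (G1).

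**Device term**

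The model in G2 for patient i, with y the rate of edema reduction, is

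y_i = b0 + b1·activity_i + b2·BMI_i + b3·ABI_i + b4·SPP_i + d·device_i + e_i.

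If the device is coded yes/no, device_i = 1 for every patient, and the model becomes

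y_i = (b0 + d) + b1·activity_i + b2·BMI_i + b3·ABI_i + b4·SPP_i + e_i.

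Only the sum b0 + d is identified. Numerically:

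| Device coding | Columns | Rank, n=30 | Rank, n=50 |
|---|---|---|---|
| 1 for everyone | 6 | 5 | 5 |
| Measured use (simulated hours) | 6 | 6 | 6 |

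More patients do not help, because the deficiency comes from the design. The coefficients b1 to b4 are unaffected: dropping the device column leaves the same fitted model. Software that drops the column reports no device coefficient. Software that keeps it has to divide b0 + d by a convention. The value printed then depends on how the device is coded and on whether the covariates are centred. With centred covariates, b0 + d is the mean change at average covariate values. With uncentred covariates it is an extrapolation to a patient with zero activity, BMI, ABI and SPP. Neither isolates the device.

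With a varying measure of use, the term is estimable, with residual degrees of freedom 30 − 6 = 24 or 50 − 6 = 44.

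**Fisher's test on paired data**

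Suppose, as an assumption, that edema is recorded as present or absent at baseline and at week 4, tested two-sided at 0.05. Fisher's test is applied to the two sets of totals and exact McNemar to the patients who change. Rejection rates come from full enumeration of the four-cell multinomial.

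For the main illustration, 90% have edema at baseline, 20% of those resolve, and 5% of the remaining 10% develop it:

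- present at both: 0.90 × 0.80 = 0.72
- resolved: 0.90 × 0.20 = 0.18
- new onset: 0.10 × 0.05 = 0.005
- absent at both: 0.10 × 0.95 = 0.095

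| Scenario (all rates assumed) | Fisher, n=30 | McNemar, n=30 | Fisher, n=50 | McNemar, n=50 |
|---|---|---|---|---|
| Power: 90% at baseline, as above | 21% | 42% | 53% | 85% |
| Power: 100% at baseline, 20% resolve | 57% | 57% | 95% | 95% |
| No change: 50% prevalence, correlation +0.5 | 0.2% | 1.8% | 0.3% | 2.5% |
| No change: 50% prevalence, correlation −0.4 | 6.3% | 2.9% | 7.6% | 3.3% |

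The third row, with positive correlation, shows the expected direction: Fisher's test rejects far less often than its nominal level. The fourth row shows that this is not guaranteed, but negative within-patient correlation is unlikely for edema.

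If the test was instead meant for a single proportion of responders, there is no second group. The 2×2 table has an empty row, and Fisher's test returns p = 1 whatever the data.

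**The case against.** The strongest defence is that the device term means use rather than receipt. Section D speaks of continuous use, F2 downloads insole data to check compliance, and Section H1 (Potential Risks) says the battery must be charged daily, so use could differ between patients. A use measure would be estimable. This stands as a possible intention, and it is why the point is limited to a yes/no term. But G2 defines no such variable, and F2 lists downloads only at 48 hours and 1 week, so the 4-week endpoint period is not covered. Either reading needs an edit.

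A second defence is that the Fisher figures rest on a binary outcome and on rates that the plan does not state. That is correct, and they are offered only as illustration. The loss disappears if all patients have edema at baseline, which is the population described in Aim 1 and F1. The inclusion list does not itself require edema, so less than 100% is possible but not established. The mismatch between an independent-groups test and repeated measurements on the same patients does not depend on these rates.

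Third, this is a pilot with a suitable paired test already planned, and an ANOVA on an intra-subject outcome can naturally be read as repeated-measures. Both points stand and limit the severity.

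**Conclusion.** Two analyses named for H1 are wrong as written. As a yes/no term, the device has no estimable coefficient in this single-arm design, whatever the sample size. Fisher's exact test does not suit a comparison of patients with themselves. The first result is algebraic and assumes only that receipt of the device is what is coded. The size of the second depends on assumed rates: power is about halved at n=30 in the 90% illustration, and nothing is lost if everyone has edema at baseline.

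Stronger readings are tempting, but the documents do not support them:

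- That the H1 analysis fails as a whole. It does not: the paired t-test, the other regression coefficients and the between-patient Fisher test for neuropathy are untouched. The last needs only that both variables be categorised.
- That the regression would yield a spurious significant device effect. What is printed depends on software, coding and centring, none of which the plan specifies. Rescaling the covariates does not change the device p-value; centring does.
- That Fisher's test would inflate false positives. With the positive correlation to be expected here, it is usually conservative.

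G2 also leaves unanswered the form's question "Which is the PRIMARY comparison/analysis". Section D and the visit schedule in F2 differ on when edema is measured. A before-after change without a control cannot be attributed to the device. These are separate points and add no weight to this one. Severity is minor to moderate.

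**What to change.** 1. In the H1 regression, do one of two things: delete the device term, or replace it with a defined measure of device use covering the 4 weeks, reported as a non-randomised association and not as the device effect.
2. Remove Fisher's exact test from the within-patient comparison. Use exact McNemar only if a binary edema outcome is defined. The Fisher test for neuropathy can stay.
3. State that the paired t-test already planned, applied to the baseline-to-4-week change in one named continuous edema measure, decides H1. Volume is a natural candidate, because Section D gives it as the direct measure.

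Deleting the term and removing the test are wording changes. Item 3 also requires choosing one measure among those that F2 allows. The use option needs a further data download at Visit 4, and the documents do not say what a download contains. The downside is that the plan gives up testing the yes/no device term as an independent predictor, which this design cannot do in any case.

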Other assessments: Other relevant assessments are Demographic/Health questionnaire, the Mini-Metal State Exam, the mobility-tiredness scale, Barthel Index, Depression Scale, fear of falling (Short-Falls Efficacy Scale – International)[25], quality of life (SF-12 Health Survey)[26], Fried Frailty Criteria, Foot Questionnaire, Pain Assessment, Fall Log and Contact Agreement, Physical activity log, follow-up questionnaire, and Shoe-fit test

AVEX insole: The AVEX insole will be given to the subject. The research personnel will adjust the clutching reel (BOA technology) in order to ensure a comfortable shoe fit. The research personnel will also provide device education to the subject and will answer any questions which may arise.

Study Day 1, Visit 2 48-hour follow up: All participants will be asked to return to clinic approximately 48 hours after visit 1. In this visit, (1) any adverse events will be assessed; (2) activity measurement (body sensor) will be returned; (3) AVEX insole data will be downloaded to ensure operability and patient compliance; and (4) further device education will be provided in case any issues have risen

Study Day 2, Visit 3 1-week follow-up: All participants will be asked to return to clinic approximately 1 week after visit 1. In this visit, (1) any adverse events will be assessed; and (2) AVEX data download to ensure operability and patient compliance. Device education will be provided if needed. The subject will be asked to return the device at their next visit. Similar assessments performed during visit 1 may be performed again during this visit.

Study Day 3, Visit 4 4-week follow-up: All participants will be asked to return to clinic approximately 4 weeks after visit 1. In this visit, outcome assessment using similar assessments described for Study Day 0 will be performed. In addition, benefit and user-friendliness of the AVEX insoles and Boa Technology 'Clutch Reel' will be assessed using a questionnaire. The subject will return the device back to the research personnel.

Patients will be asked to wear a comfortable shirt which holds a small activity monitor (PAMSys) for a period of 48 Hours (2 days). Patients will be requested to return this device via a pre-paid FEDEX envelope

Study Day 4, Visit 5 Three month follow-up: All participants will be contacted by the study coordinator approximately three months post the last study visit (Visit 4) to document potential incident of diabetic foot ulcer or falls.

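### Sensor activity is a predictor of response in H1 and H2 but an outcome in H3, and no 48-hour recording is scheduled before the insole is dispensed

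*Combined protocol and SAP*

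**What the plan says.** Section G2 gives the same variables different roles in different hypotheses.

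- **H1.** A multiple linear regression is to show whether "level of activity, BMI, ABI, Skin perfusion pressure, and micro-mobile foot compression device are independent predictors for the rate of edema reduction".
- **H2.** The similar plan is applied by "considering change in Skin perfusion pressure and ABI as dependent variables", and the predictors are "severity of neuropathy quantified using Semmes Weinstein Monofilament, the level of activity, BMI, and age".
- **H3.** "The dependent variables will be number of total steps per day, duration of walking and standing, duration of longest episode of walking", followed by further sensor measures and the SF12.

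Section D expects the device to change these variables. For circulation it says "We expect to see positive changes in ABI and SPP measurements", and Hypothesis 3 expects activity to improve against baseline. G2 does not say whether any predictor is a baseline, follow-up or change value.

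On timing, Section D declares 48-hour activity at baseline and 4 weeks. In Section F2, handing over the insole is part of Visit 1. At Visit 2, about 48 hours later, "activity measurement (body sensor) will be returned" and insole data are downloaded to check compliance. At Visit 4 the subject gives the device back; a 48-hour shirt-sensor period is described next, with the sensor returned by post. ABI and SPP are measured at the Study Day 0 baseline.

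**The concern.** A predictor of response should be fixed before treatment can act on it. If a patient's swelling falls and the patient walks more as a result, a regression of edema reduction on activity recorded after dispensing will tend to show activity as a predictor, although the effect runs the other way. The other coefficients in that model (BMI, ABI and SPP in H1; neuropathy, BMI and age in H2) are then adjusted for something that is partly a consequence of response. The data cannot separate the two directions afterwards.

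Section G1 says the pilot is meant to inform a larger superiority trial. A spurious finding that active patients respond better could carry over into that trial's selection criteria or covariates.

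**Working it through.** **1. Roles, side by side (G2)**

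| Variable | H1 | H2 | H3 |
|---|---|---|---|
| Activity | predictor | predictor | outcome |
| ABI | predictor | outcome (change) | – |
| SPP | predictor | outcome (change) | – |

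I read activity as the sensor measure, because H3 defines it by steps, walking and standing. The physical activity log listed in F2 has no timing and no role in G2.

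**2. Is there a pre-device value (F2)?**

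- *ABI and SPP:* yes, at Visit 1.
- *First activity recording:* it lasts 48 hours and the sensor comes back about 48 hours after Visit 1, when the insole was given out. No earlier sensor period is described. The compliance download at Visit 2 implies that the insole is meant to be in use by then. Section D also schedules an edema measurement at 48 hours, so the plan itself looks for response within this window.
- *Second activity recording:* it appears to start after Visit 4, and so after the 4-week edema measurement it would be used to predict.

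**3. SPP.** Section D uses SPP as an indirect measure of edema, the primary endpoint. A follow-up or change value of SPP as a predictor of edema reduction would be close to circular. F2 also says SPP is unaffected by peripheral edema, which sits badly with that use.

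**4. Illustration of size.** The plan has no figure to reproduce. The following are assumptions, not from the documents:

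- all variables are standardised;
- true pre-device activity, ABI and SPP have no effect on edema reduction;
- edema reduction shifts follow-up values by b = 0.2, 0.3 or 0.5 SD;
- the first activity recording carries half of b;
- added noise has SD 0.5;
- the test is two-sided at 5%.

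The model is edema reduction on activity, ABI, SPP and BMI. The device term is left out: every patient gets the insole, so its column equals the intercept (6 columns, rank 5). Both sample sizes are used because Sections D and F1 say 30 and G1 says 50.

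Simulated false-positive rate for activity, first recording (4,000 runs per setting):

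| b | n=30 | n=50 |
|---|---|---|
| 0 | 5.2% | 4.5% |
| 0.2 | 7.0% | 8.8% |
| 0.3 | 10.4% | 15.0% |
| 0.5 | 19.5% | 32.0% |

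*Check by formula.* The implied correlation is r = 0.5b / √(1 + (0.5b)² + 0.25). For b = 0.5, r = 0.25/√1.3125 = 0.218. With three other covariates, the Fisher z mean is atanh(r) × √(n − 6):

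- n=30: 0.2218 × √24 = 1.087, rejection probability 19.2%;
- n=50: 0.2218 × √44 = 1.471, rejection probability 31.3%.

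For b = 0.2, r = 0.1/√1.26 = 0.089, giving 7.2% and 9.1%. These agree with the simulation.

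*Follow-up values of activity, ABI and SPP together.* For b = 0.2, 0.3 and 0.5, the chance that at least one of the three is falsely significant is 35%, 54% and 85% at n=30, and 51%, 77% and 98% at n=50. With true pre-device values it stays at 13% to 15%, in line with 1 − 0.95³ = 14.3% for three independent tests.

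**The case against.** The strongest reply is that this is the last-listed H1 analysis in a proof-of-concept pilot. Independent predictor usually means no more than mutually adjusted, and the plan never speaks of causes. A baseline value as predictor in one model and its change as outcome in another is ordinary practice. G2 writes change explicitly for the H2 outcomes but not for the H1 predictors, so baseline values are the natural reading. The first recording also covers only about 48 hours, before most of a 4-week edema change could occur.

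Much of this stands. It disposes of three stronger readings that a reader might infer:

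- *That no pre-device activity value exists at all.* Section D declares a baseline activity measure, F2 lists an undated activity log, and nothing states exactly when sensor or insole wear begins. The documents support only that no pre-device 48-hour sensor period is scheduled.
- *That ABI and SPP are affected in the same way as activity.* They have Visit 1 values and are at risk only if follow-up or change values are entered.
- *That false findings would be very frequent.* Assuming a correlation of 0.3 to 0.5 between activity and edema reduction gives 36% to 81% at n=30 by a two-variable Fisher z calculation. That only restates the assumed correlation, which the documents do not support, and it is not the planned regression.

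The reply does not rescue sensor activity. An analyst who sensibly chooses the baseline recording still appears to get a value taken after dispensing.

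**Conclusion.** The point holds in limited form. For sensor activity the fault lies in the schedule as well as the wording: both recordings appear to follow dispensing, so neither is a clean pre-treatment predictor in H1 or H2. For ABI and SPP the fault is only the unstated time point.

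The inflation of activity's false-positive rate is modest if the first recording is used (about 7% to 20% at n=30, 9% to 32% at n=50) and larger with follow-up values. These figures rest wholly on the assumed reverse effect of 0.2 to 0.5 SD, half of it present in the first 48 hours; with no reverse effect the rate is the nominal 5%. The conclusion about timing rests on the visit order in F2 and would change if a sensor period before dispensing were documented.

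The models concerned are secondary and exploratory. The paired comparison of edema with baseline does not use these predictors and is untouched. The change is worth making because it costs little.

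**What to change.** In Section G2:

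1. State that every H1 and H2 predictor is a value measured at Visit 1 before the insole is dispensed: ABI, SPP, BMI, age and neuropathy, each in the model that lists it.
2. Remove sensor activity from the H1 and H2 predictor models unless a pre-dispensing recording exists. If one does, F2 should say when it is taken.
3. Report the relations of activity to edema and of activity to ABI and SPP only as exploratory associations between outcomes, with no claim of prediction.

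The cost is a few sentences of analysis-plan wording and the loss of activity as an adjusted predictor, which could not have been interpreted as planned.
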